8.5. Subsequent Visits

Visit 2 – Study visit

- A review of the BG levels in the preceding week will be carried out by the study dietitian, in order to determine whether any further adjustments in insulin dose need to be made.
- The CGM will be inserted.
- Randomisation of the insulin dose order will be carried out and final dose calculations will be done by the dietitian according to the equations in section 5.3.
- Full written instructions will be provided to the participants, including insulin doses and timings for the three study meals, contact details and what to do if BG levels should be high (greater than 16mmol/L) or low (less than 4mmol/L).
- There will also be instructions about what they should do in the event of a sensor malfunction.
- The child and family will be informed that they can call the research team during office hours at any stage to discuss events during the week of the study, and they will be provided with contact details. If any advice is required outside office hours, they will be advised to contact their clinical diabetes team in the usual way.

Visit 3: End of study visit - The participant will return to their original outpatient or day-care setting and the CGM sensor will be removed by the study nurse and data downloaded onto the web-based system Diasend which is regularly used in clinics. Participants and their family will have the opportunity of viewing the download from the sensor. The participant and parent will be asked to complete the short questionnaires about the acceptability of the additional insulin doses.

8.6. Sample Handling

No samples will be taken during the trial. The only sample for eligibility is the HbA1c finger-prick sample which will be taken and managed routinely according to protocols in the relevant clinical service.

8.7. Discontinuation/Withdrawal of Participants from Trial Treatment

Each participant has the right to withdraw from the trial at any time. In addition, the Investigator may discontinue a participant from the trial at any time if the Investigator considers it necessary for any reason including:

- Pregnancy
- Ineligibility (having been overlooked at screening)
- Significant protocol deviation
- Significant non-compliance with treatment regimen or trial requirements
- Severe hypoglycaemia occurring during the trial week, whether or not this is as a result of the evening meal dose of insulin
- Withdrawal of Consent
- Loss to follow up

Any CGM data available up to the time of patient withdrawal or exclusion will be included in the data analysis.

The reason for withdrawal will be recorded in the CRF.

If the participant is withdrawn due to an adverse event, the Investigator will arrange for follow-up visits or telephone calls until the adverse event has resolved or stabilised.

8.8. Definition of End of Trial

The end of trial is the date of the last visit of the last participant.

9. INVESTIGATIONAL MEDICINAL PRODUCT (IMP)

9.1. IMP Description

The trial IMP is Insulin Aspart (NovoRapid). This is provided to the participant as part of normal standard care. The trial medication will be dispensed according the standard procedures at each site and is being used in its normal indication and standard therapeutic dose. The only change in this study is the insulin dosage around the evening meal.

9.2. Storage of IMP

No specific storage requirement above those stated for standard care are required for the IMP in this trial. There will be no temperature monitoring for the IMP.

9.3. Compliance with Trial Treatment

Participants and their families will be asked to complete a diary including the actual insulin doses given. This will be viewed at the end of the study and data may be removed from analysis if significant non-compliance has occurred, for example the advised dose was not given, or the timing was not accurate to within 15 minutes.

9.4. Accountability of the Trial Treatment

IMP is supplied as part of normal standard care and therefore no accountability records will be maintained for the trial.

9.5. Concomitant Medication

Any glucose-containing medication is contraindicated.

9.6. Post-trial Treatment

Not relevant for this trial

10. SAFETY REPORTING

10.1. Definitions

Adverse Event (AE)	Any untoward medical occurrence in a participant to whom a medicinal product has been administered, including occurrences which are not
--------------------	---

	necessarily caused by or related to that product.
Adverse Reaction (AR)	
An untoward and unintended response in a participant to an investigational medicinal product which is related to any dose administered to that participant.
 
The phrase "response to an investigational medicinal product" means that a causal relationship between a trial medication and an AE is at least a reasonable possibility, i.e. the relationship cannot be ruled out.
 
All cases judged by either the reporting medically qualified professional or the Sponsor as having a reasonable suspected causal relationship to the trial medication qualify as adverse reactions.

Serious Adverse Event (SAE)	
A serious adverse event is any untoward medical occurrence that:
 
 • results in death • is life-threatening • requires inpatient hospitalisation or prolongation of existing hospitalisation • results in persistent or significant disability/incapacity • consists of a congenital anomaly or birth defect. 
Other 'important medical events' may also be considered serious if they jeopardise the participant or require an intervention to prevent one of the above consequences.
 
NOTE: The term "life-threatening" in the definition of "serious" refers to an event in which the participant was at risk of death at the time of the event; it does not refer to an event which hypothetically might have caused death if it were more severe.

Serious Adverse Reaction (SAR)	An adverse event that is both serious and, in the opinion of the reporting Investigator, believed with reasonable probability to be due to one of the trial treatments, based on the information provided.
Suspected Unexpected Serious Adverse Reaction (SUSAR)	
A serious adverse reaction, the nature and severity of which is not consistent with the information about the medicinal product in question set out:
 
 • in the case of a product with a marketing authorisation, in the summary of product characteristics (SmPC) for that product • in the case of any other investigational medicinal product, in the investigator's brochure (IB) relating to the trial in question.

NB: to avoid confusion or misunderstanding of the difference between the terms "serious" and "severe", the following note of clarification is provided: "Severe" is often used to describe intensity of a specific

event, which may be of relatively minor medical significance. “Seriousness” is the regulatory definition supplied above.

Any pregnancy occurring during the clinical trial and the outcome of the pregnancy should be recorded and followed up for congenital abnormality or birth defect, at which point it would fall within the definition of “serious”.

10.2. Causality

The relationship of each adverse event to the trial medication must be determined by a medically qualified individual according to the following definitions:

Related: The adverse event follows a reasonable temporal sequence from trial medication administration. It cannot reasonably be attributed to any other cause.

Not Related: The adverse event is probably produced by the participant's clinical state or by other modes of therapy administered to the participant.

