7.2. Inclusion Criteria

- Diagnosis of Type 1 diabetes (for at least a year)
- Aged 6 to under 18 years.
- On multiple daily insulin injections, including basal long-acting insulin and rapid-acting insulin before each meal.
- HbA1c < 75 mmol/mol (9.0%)
- Participant and/or parent/legal guardian willing and able to give informed consent for participation in the study.
- Family have a freezer in which to safely store the test meals.
- In the Investigator's opinion, is able and willing to comply with all trial requirements.

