10.3. Procedures for Recording Adverse Events

As insulin is a well-known IMP, not all non-serious AEs will be recorded. Mild hypoglycaemia responding to treatment does not need to be reported as an AE, but will be recorded on the daily diary as well as on the CGM records.

Children with Type 1 diabetes are always at risk of hypoglycaemia which may result in hospitalisation. It is not anticipated that the project would increase the risk of severe hypoglycaemia (a low blood glucose level that is associated with unconsciousness or convulsion) but a child/young person may have one of these episodes during the study. The participants will all be wearing a continuous glucose monitor with an alarm if the BG becomes low or high. The alarm will therefore warn the participant and family if the BG level falls below a certain level, reducing the risk of severe hypoglycaemia. However severe hypoglycaemia resulting in unconsciousness or convulsions would be reported immediately as a SAE (see below).

The child and family will be informed that they can call the research team during office hours at any stage to discuss events during the week of the study, and they will be provided with contact details. If any advice is required outside office hours, they will be advised to contact their clinical diabetes team in the usual way.

It is not anticipated that the CGM will cause any adverse effects. However infection or inflammation at the insertion site would be reported at the end of the trial as an AE. If the sensor stops working or needs to be replaced for any reason during the trial week, this does not need to be reported as an AE, but the participant or family will contact the research team to have it re-sited.

The following information will be recorded for all reportable AEs: description, date of onset and end date, severity, assessment of relatedness to trial medication, other suspect drug or device and action taken. Follow-up information should be provided as necessary.

AEs considered related to the trial medication as judged by a medically qualified investigator or the Sponsor will be followed either until resolution, or the event is considered stable.

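### Section 10.2 requires that no other reasonable cause exists before an event is 'Related', which conflicts with the lower AR and differing SAR thresholds in section 10.1

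*Combined protocol and SAP*

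**What the plan says.** Section 10.1 defines an adverse reaction as a response for which a causal relationship with the trial medication "is at least a reasonable possibility, i.e. the relationship cannot be ruled out". It adds that a reasonable suspicion held by either the reporting medically qualified professional or the sponsor is enough. For a serious adverse reaction, the same table asks whether the event is, in the reporting investigator's opinion, "believed with reasonable probability to be due to one of the trial treatments".

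Section 10.2 then prescribes the definitions by which a medically qualified person must judge each event. 'Related' has two conditions: "The adverse event follows a reasonable temporal sequence from trial medication administration", and "It cannot reasonably be attributed to any other cause". 'Not Related' reads: "The adverse event is probably produced by the participant's clinical state or by other modes of therapy administered to the participant". There is no third category.

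Section 10.3 attaches a duty to the result: "AEs considered related to the trial medication as judged by a medically qualified investigator or the Sponsor will be followed either until resolution", or until the event is considered stable.

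Two facts about the population bear on this. Section 9.1 names insulin aspart as the trial product. Section 7.2 requires every participant to be "On multiple daily insulin injections, including basal long-acting insulin and rapid-acting insulin before each meal", so each child also takes a second insulin that is not the trial product.

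**The concern.** The 10.1 adverse-reaction definition asks whether the trial insulin could have caused the event. The 10.2 rule asks whether anything else reasonably could have. For an event with one candidate cause the two agree. For an event with several they can give opposite answers, and nothing says which section prevails.

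Hypoglycaemia is the reaction of most interest here, and a competing explanation is often available. All participants take basal insulin, section 6.3 allows its dose to be adjusted in the run-in week, and section 10.3 describes these children as always at risk of lows. Section 10.3 also asks for any other suspect drug to be recorded for each reportable event, so the form expects more than one suspect. Under 10.2, a single reasonable alternative is enough to defeat 'Related'.

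At stake is whether two assessors, each following the protocol, would classify the same reportable event in the same way, and whether drug-related harm could be under-called.

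**Working it through.** No calculation underlies the conflict itself, so the check sets the definitions side by side and then traces where the relatedness judgement is used.

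**Step 1. Apply each definition to four kinds of event**, all assumed to fit in time with the aspart dose.

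| Event | 10.1 adverse reaction | 10.2 category | 10.1 SAR, if serious |
|---|---|---|---|
| A. Aspart plausible, no other reasonable cause | Yes | Related | Yes |
| B. Aspart plausible, another cause reasonable but not probable | Yes | Neither | Depends on the investigator's view of probability |
| C. Aspart cannot be ruled out, another cause probable | Yes | Not Related | Probably not |
| D. Aspart ruled out, another cause probable | No | Not Related | No |

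The sections agree on A and D. In C they contradict each other. In B the event is an adverse reaction under 10.1 but has no category in 10.2. B and C are the events with more than one plausible cause.

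**Step 2. A concrete case.** A child has a severe low overnight after a test meal, and the long-acting dose had been raised in run-in. The aspart dose cannot be ruled out, so 10.1 makes the event an adverse reaction. If the assessor thinks the basal change a reasonable explanation, 10.2 does not allow 'Related'. If the basal change is not thought the probable explanation, 10.2 does not allow 'Not Related' either.

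**Step 3. Where relatedness is used.**

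- Dependent on it: adverse-reaction and SAR status (10.1), any SUSAR assessment that follows (10.6), and the follow-up of related events (10.3).
- Not dependent on it: reporting of severe hypoglycaemia as an SAE (10.3, 10.4), safety group review of all SAEs (10.7), the termination rule of two severe lows on an arm (11.4), and severe hypoglycaemia as a ground for discontinuation (8.7), which applies whatever the cause. Tertiary objective 2 (section 5) counts every episode below 4 or above 12 mmol/l.

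**Step 4. How many events.** Section 11.4 gives a background rate of 10 severe lows in 340 patients per year.

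- Rate: 10 / 340 = 0.0294 per patient-year.
- Exposure: 40 children × 7 / 365 = 0.767 patient-years.
- Expected severe lows in the trial week: 0.0294 × 0.767 = 0.023, or about 0.02.

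This assumes no added risk. If the true rate were ten times the background, purely as an illustration, the figure would be about 0.23. Neither figure includes other reportable events, such as a low that does not respond to treatment, for which the documents give no rate.

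**The case against.** The best defence is that 10.2 does not govern adverse-reaction status. Section 10.1 has its own operative sentence, under which a reasonable suspicion by either the reporting professional or the sponsor suffices, and the SAR definition has its own test. The important protections also do not turn on causality: a severe low is reported at once, reviewed, counted for stopping, and may lead to discontinuation whatever its cause. If the child is withdrawn for it, sections 8.7 and 10.3 require follow-up regardless of relatedness. All of this stands and limits the consequence. It does not remove the conflict, because 10.2 says its definitions must be applied to each event, and the follow-up sentence in 10.3 depends on a relatedness judgement.

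A reader might go further and infer that almost every hypoglycaemic event would fail the 10.2 test because every child takes basal insulin. The documents do not support that. Mild hypoglycaemia that responds to treatment is not a reportable event, and relatedness is recorded only for reportable ones. For the rest, the test is a medical judgement: universal use of basal insulin does not make it a reasonable attribution for a particular low. Appendix B gives reduced hypoglycaemia risk as the reason for lowering the added dose, so an assessor could well attribute an early low to that dose. Nor is failing 'Related' the same as being 'Not Related'.

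A reader might also infer that tertiary objective 2 would be biased, or that SUSARs would be missed. The first is wrong, because that outcome ignores cause. The second is not shown: a SUSAR must also be inconsistent with the product's summary of characteristics, which is not among the documents.

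**Conclusion.** The causality wording is wrong as written. Sections 10.1 and 10.2 set three different thresholds for the same judgement, and the two categories in 10.2 do not cover every event. A reportable event with more than one plausible cause can be an adverse reaction in one section and 'Not Related', or unclassified, in the next.

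The effect is confined to adverse-reaction and SAR classification, what follows from it for SUSAR assessment, and one follow-up duty. It does not touch the efficacy analysis. The number of events affected is likely to be small, on the assumption that the section 11.4 background rate is roughly right and not greatly raised by the added dose. The documents give no breakdown of events by cause, so the share that would be misclassified cannot be estimated. The correction is still worth making, because causality assessment in a paediatric drug trial should not depend on which of two adjacent sections the assessor reads.

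**What to change.** Use one threshold in all three places.

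- In 10.2, define 'Related' as a causal relationship with the trial insulin that is at least a reasonable possibility and cannot be ruled out, and 'Not Related' as a relationship that can be ruled out. Section 10.1 already treats reasonable possibility and not being ruled out as equivalent, so the two categories are then complementary and the gap closes.
- In 10.1, replace reasonable probability in the SAR definition with the same threshold. Changing 10.2 alone would leave this third standard in place.
- Add a sentence that concurrent basal insulin, or diabetes itself, does not by itself make an event 'Not Related'.

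With these changes, events A, B and C in the table are 'Related' and D is 'Not Related', in agreement with 10.1. The cost is a few sentences in a protocol amendment. Somewhat more events will be classed as related, as the 10.1 adverse-reaction definition already implies. Nothing in dosing, clinical management or the analysis changes.

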10.3. Procedures for Recording Adverse Events

As insulin is a well-known IMP, not all non-serious AEs will be recorded. Mild hypoglycaemia responding to treatment does not need to be reported as an AE, but will be recorded on the daily diary as well as on the CGM records.

Children with Type 1 diabetes are always at risk of hypoglycaemia which may result in hospitalisation. It is not anticipated that the project would increase the risk of severe hypoglycaemia (a low blood glucose level that is associated with unconsciousness or convulsion) but a child/young person may have one of these episodes during the study. The participants will all be wearing a continuous glucose monitor with an alarm if the BG becomes low or high. The alarm will therefore warn the participant and family if the BG level falls below a certain level, reducing the risk of severe hypoglycaemia. However severe hypoglycaemia resulting in unconsciousness or convulsions would be reported immediately as a SAE (see below).

The child and family will be informed that they can call the research team during office hours at any stage to discuss events during the week of the study, and they will be provided with contact details. If any advice is required outside office hours, they will be advised to contact their clinical diabetes team in the usual way.

It is not anticipated that the CGM will cause any adverse effects. However infection or inflammation at the insertion site would be reported at the end of the trial as an AE. If the sensor stops working or needs to be replaced for any reason during the trial week, this does not need to be reported as an AE, but the participant or family will contact the research team to have it re-sited.

The following information will be recorded for all reportable AEs: description, date of onset and end date, severity, assessment of relatedness to trial medication, other suspect drug or device and action taken. Follow-up information should be provided as necessary.

AEs considered related to the trial medication as judged by a medically qualified investigator or the Sponsor will be followed either until resolution, or the event is considered stable.

It will be left to the Investigator's clinical judgment to decide whether or not an AE is of sufficient severity to require the participant's removal from treatment. A participant may also voluntarily withdraw from treatment due to what he or she perceives as an intolerable AE. If either of these occurs, the participant must undergo an end of trial assessment and be given appropriate care under medical supervision until symptoms cease, or the condition becomes stable.

10.4. Reporting Procedures for Serious Adverse Events

All SAEs (other than those defined in the protocol as not requiring reporting) must be reported on the Oxford University Hospitals NHS Trust SAE reporting form to OUH study team within 24 hours of the Site Study Team becoming aware of the event by email or fax.

Once the SAE has been received the OUH study team will forward the report to the R&D office immediately. **SAE reports should be faxed or emailed to: [name] or [contact]**

R&D will perform an initial check of the report, request any additional information, and ensure it is reviewed by the Medical Monitor on a weekly basis. It will also be reviewed at the next Trial Safety Group meeting. All SAE information must be recorded on an SAE form and faxed, or scanned and emailed, to R&D. Additional and further requested information (follow-up or corrections to the original case) will be detailed on a new SAE Report Form and faxed/emailed to R&D.

10.5. Expectedness

Expectedness will be determined according to the Summary of Product Characteristics.

10.6. SUSAR Reporting

All SUSARs will be reported by the CI to the relevant Competent Authority and to the REC and other parties as applicable. For fatal and life-threatening SUSARS, this will be done no later than 7 calendar days after the Sponsor or delegate is first aware of the reaction. Any additional relevant information will be reported within 8 calendar days of the initial report. All other SUSARs will be reported within 15 calendar days.

Principal Investigators will be informed of all SUSARs for the relevant IMP for all studies with the same Sponsor, whether or not the event occurred in the current trial.

10.7. Safety Monitoring Committee

The Oxford University Hospitals Trust / University of Oxford Trials Safety Group (TSG) will conduct a review of all SAEs for the trial reported during the quarter and cumulatively. The aims of this committee include:

- To pick up any trends, such as increases in un/expected events, and take appropriate action
- To seek additional advice or information from investigators where required
- To evaluate the risk of the trial continuing and take appropriate action where necessary

